10. STATISTICAL CONSIDERATIONS

10.1 DESCRIPTION OF STATISTICAL METHODS

Wound area will be analyzed for size, percentage closure on weekly basis. The mean, median and standard deviations will be calculated and scatter plots developed to determine healing rates by application number, and days in treatment. The mean number of application of product will be tabulated.

All statistical tests to examine the change from baseline (study pre-treatment) will be conducted using a type 1 error rate of 5%. Simultaneous testing for the 2 primary endpoints will be conducted based on individual a priori thresholds. The analyses of the secondary endpoints will be conducted without adjustment for multiple testing.

The analysis of the primary endpoints will be based on a generalized linear model specifying the distribution as binomial. If a patient withdraws prior to completing the study, however the last recorded observation revealed the wound had closed, the patient will be counted in the primary analysis as having achieved complete wound epithelization. If a patient withdraws prior to the 12-week wound evaluation visit and the last recorded observation revealed the wound had not closed, the patient will be counted in the primary analysis as not having achieved complete wound epithelization. This procedure will also be followed for the examination of the patients by the various percent reduction thresholds. The analyses of all non-primary endpoints will be based on the distribution of data. For continuous variables, descriptive statistics will be used and the change from baseline will be tested against a difference of zero. For binomial and multinomial variables, results will be presented using counts, percentages, and shift tables. The analysis of the time of the initial observation of complete wound epithelization will be reported using Kaplan-Meier estimates. The sample size for this clinical investigation was derived based on establishing sufficient precision among the different endpoints to be able to reliably estimate the expected effect of the 2 product used either alone or in combination. For proportions, the length of the 2-sided 95% confidence interval from the proportion to the limit with 80 patients is between 9% and 10% (ref. table presented below).

Scenario	Lower 95% Exact Confidence Limit (%)	Percentage of Patients Who Respond	Upper 95% Exact Confidence Limit (%)
1	15.99	25.00	35.94
2	26.92	37.50	49.04
3	30.33	40.00	50.28
4	50.96	62.50	73.08

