5	64.06	75.00	84.01

For mean changes from baseline, if the standard deviation of the difference from baseline for a parameter is 10 units, the confidence level will exceed 90% with a distance from the mean to the limit as small as 2 units.

For data derived from a binomial distribution and a continuous distribution, 80 patients should be sufficient to detect a clinically-meaningful change in this clinical investigation.

In summary, the sample size for this clinical investigation is sufficient to detect a 34% difference in the proportion of responders between the 2 treatments (power: 81.9%, alpha: 5%, 40 patients per treatment arm with 30% response and 64% response, respectively). If the observed proportion of response between the 2 treatment arms is 15% and 46% respectively, with 40 patients per treatment arm, the power will be 81.1%. If there is an imbalance between the 2 treatment arms (30 patients and 50 patients, respectively), and observed proportion of response between the 2 treatment arms is 15% and 47%, the power will be 80.3%.

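### The stated precision of 9% to 10% with 80 patients contradicts the plan's own table (9.01 to 11.54 points), and the 40% row fits 40/100 rather than 32/80.

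*Combined protocol and SAP*

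**What the plan says.** Section 10.1 (Description of Statistical Methods) rests the sample size on precision: "The sample size for this clinical investigation was derived based on establishing sufficient precision among the different endpoints". For proportions it then gives one figure, "For proportions, the length of the 2-sided 95% confidence interval from the proportion to the limit with 80 patients is between 9% and 10" per cent, and points to the table that follows.

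The table has five scenarios. Each gives a response rate between a lower and an upper limit, and the columns are headed as exact limits ("Lower 95% Exact Confidence Limit" and its upper counterpart). Scenario 1 reads "15.99 25.00 35.94", scenario 2 "26.92 37.50 49.04", scenario 3 "30.33 40.00 50.28" and scenario 5 "64.06 75.00 84.01". Scenario 4 is 62.50% with limits 50.96 and 73.08. No row carries its own sample size. The only one attached to the table is the 80 patients of the introducing sentence.

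**The concern.** The sentence and the table describe the same quantity, so they should agree, and simple subtraction shows that they do not. Row 3 also looks wrong without any software. At a fixed sample size the interval widens as the rate approaches 50%, so 40% must have a wider interval than 37.5%. The printed row 3 is narrower than row 2.

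Both primary endpoints in section 4.1.1 are proportions. This sentence and table are the precision argument for proportions in a plan that says its size was chosen for precision. A reader who takes the sentence at its word expects limits no more than 10 points from the estimate. Both faults make the precision look better than it is.

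**Working it through.** **Inputs, all from section 10.1:** n = 80; two-sided 95% confidence; exact limits; response rates 25, 37.5, 40, 62.5 and 75%.

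**Step 1. Distances as printed.** Distance below = rate − lower limit; distance above = upper limit − rate; width = upper − lower.

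| Row | Rate (%) | Printed limits | Below | Above | Width |
|---|---|---|---|---|---|
| 1 | 25.00 | 15.99, 35.94 | 9.01 | 10.94 | 19.95 |
| 2 | 37.50 | 26.92, 49.04 | 10.58 | 11.54 | 22.12 |
| 3 | 40.00 | 30.33, 50.28 | 9.67 | 10.28 | 19.95 |
| 4 | 62.50 | 50.96, 73.08 | 11.54 | 10.58 | 22.12 |
| 5 | 75.00 | 64.06, 84.01 | 10.94 | 9.01 | 19.95 |

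Three of the ten distances lie between 9 and 10 (9.01, 9.67, 9.01). The other seven exceed 10, and the largest is 11.54. Rounding to whole points does not help: 10.58 and 10.94 become 11, and 11.54 becomes 12.

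**Step 2. Reproduce the limits at n = 80.** The Clopper-Pearson limits for x responders are: lower = 0.025 quantile of Beta(x, n − x + 1); upper = 0.975 quantile of Beta(x + 1, n − x).

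| Row | x/80 | Exact limits | Agrees with the table? |
|---|---|---|---|
| 1 | 20/80 | 15.99, 35.94 | yes |
| 2 | 30/80 | 26.92, 49.04 | yes |
| 3 | 32/80 | 29.20, 51.56 | **no** (printed 30.33, 50.28) |
| 4 | 50/80 | 50.96, 73.08 | yes |
| 5 | 60/80 | 64.06, 84.01 | yes |

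Four rows reproduce to two decimals, which confirms both the method and n = 80. Row 3 does not.

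**Step 3. Where row 3 comes from.** Among all x/n equal to 40.00% with n from 20 to 299, only 40/100 gives 30.33 and 50.28.

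**Step 4. Size of the row 3 difference.** At n = 80 the distances are 40.00 − 29.20 = 10.80 and 51.56 − 40.00 = 11.56, and the width is 51.56 − 29.20 = 22.36. The printed width is 19.95. The difference is 22.36 − 19.95 = 2.41 points, and 2.41/22.36 is about 11%. With row 3 recomputed, the n = 80 distances over the five rates run from 9.01 to 11.56.

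**Step 5. Could another interval explain the sentence?** The normal-approximation half-width is 1.96 × √(p(1 − p)/80). It gives 9.49 points at 25% and 75%, 10.61 at 37.5% and 62.5%, and 10.74 at 40%. At n = 80 the other methods range as follows: Wilson 8.19 to 10.95, Agresti-Coull 8.26 to 10.97, Jeffreys 8.49 to 10.93, inverted exact test 8.42 to 11.26. Exact limits at n = 100 range from 8.12 to 10.28, taking 37.5% and 62.5% as 38/100 and 62/100. None stays within 9 to 10.

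**Step 6. Rates outside the table.** At 15%, a rate used in the power scenarios of the same section, 12/80 gives 8.00 to 24.74, with distances of 7.00 and 9.74. Any restated range must therefore be tied to the tabulated rates.

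The adjacent claim about mean changes is sound: 2 × √80/10 = 1.789, which corresponds to 92.6% confidence (normal) or 92.3% (t, 79 df), above the stated 90%.

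**The case against.** The arithmetic is hard to dispute; the case against concerns its weight.

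- **No target is breached.** The plan sets no maximum half-width, the lower end of its range is right, and the upper end is off by about 1.6 points. Four of five rows print correct n = 80 limits directly below the sentence, so a careful reader can see the true distances. This stands, and it keeps the point modest.
- **Row 3 may be deliberate.** Maximum enrolment is 100 (section 10.2), so the row could be an unlabelled maximum-enrolment scenario, and the fault would then be a missing label. This is possible, and n = 100 is only an inference from the matching limits. But the sentence introducing the table says 80 patients, so an unlabelled n = 100 row would still be inconsistent with it.
- **The sentence may mean the average half-width.** Half the printed width is 9.975 in rows 1, 3 and 5, but 11.06 in rows 2 and 4, so this reading fails too.
- **The count of seven in ten mixes sample sizes**, because it includes row 3. It is correct as a description of the printed table. For n = 80 alone it is six of eight in the four sound rows, or eight of ten with row 3 recomputed. The conclusion is the same.
- **The table is not the whole case for proportions.** Section 10.1 also gives two-arm power scenarios, and the primary endpoints are defined for each wound type, whereas the table describes all 80 patients together. Both remarks are fair. The correction here concerns the pooled figure only.

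**Conclusion.** The concern holds. The stated range of 9% to 10% is wrong against the table it cites: the printed distances reach 11.54 points, and the n = 80 distances at the tabulated rates run from 9.01 to 11.56. Row 3 is not an exact interval for 80 patients; if n = 80 was intended, its width is understated by 2.41 points.

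The contradiction between sentence and table rests on the printed numbers alone. The finding on row 3 assumes Clopper-Pearson limits, which the exact label and the agreement of the other four rows support. This should be fixed because it is a wrong figure in the stated justification of the sample size. It does not show that 80 patients are too few.

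**What to change.** In section 10.1:

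1. Restate the range as *between about 9.0 and 11.6 percentage points for the response rates tabulated*.
2. Replace row 3 with 29.20 / 40.00 / 51.56, or, if 100 patients were intended, keep the printed limits and label the row n = 100.
3. Put the sample size in the table heading.

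The cost is one sentence, one table row and a heading, and the stated precision becomes slightly less favourable. Patient numbers, analyses and tests stay as they are.

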Study Design:	
This study is a single-site, prospective, observational clinical study of Cytal® Wound Matrix alone or in combination with MicroMatrix® for the management of wounds.
 
In this study, Cytal® Wound Matrix 1-Layer will be applied topically to study wounds, with MicroMatrix® applied to fill the base of deep wounds (exceeding 3mm in depth) according to product use instructions. Patients with diverse wound types will be observed in the study, including patients with venous ulcers, diabetic foot ulcers, pressure ulcers, trauma wounds, external surgical wounds, and wound dehiscence/surgical site infection.
 
Patients may undergo weekly treatment for their wounds and can be treated with up to 10 applications of Cytal® (with MicroMatrix® when wound depth exceeds 3mm) within the first 12 weeks, including unscheduled visits (within this 12 week period). If the Subject has multiple wounds, the most-appropriate wound that meets inclusion criteria and has at least two cm of healthy tissue between itself and other wounds (as determined by the investigator) will be selected as the Study Wound. A protocolized standard of care will be followed for Study Wounds in addition to the application of Cytal® and MicroMatrix® (i.e. surgical debridement, offloading etc. as appropriate for the particular wound type and severity).

Objectives:	
Primary Objective
 
The primary objective is to assess the effect of Cytal® with or without MicroMatrix® on primary measures of wound healing efficacy.
 
Secondary Objective(s)
 
 1. Assess the effect of Cytal® with or without MicroMatrix® on secondary measures of wound healing efficacy. 2. Assess effect of treatment on patient-reported quality of life at baseline and at time of healing or at 12 weeks if the wound remains unhealed. 3. Assess complete wound management. 4. Wound-related adverse events. 
Tertiary Objective(s)
 
 1. Assess costs of treatment and patient work status.

	
2. Assess wound pathology.

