	
 3. Subject is willing and able to adhere to protocol requirements and agrees to participate in the study program and comply with the study follow-up regimen. 4. Subject or legal representative is willing to provide informed consent. 5. For females of reproductive potential, confirmed negative pregnancy test at enrollment. 
Exclusion Criteria: (No exclusion criteria may meet for enrollment)
 
 1. Allergy or hypersensitivity to materials in porcine-based study products (per subject report) or personal preference. 2. Subject report of concurrent participation in another clinical trial that involves an investigational drug or device that would interfere with this study. 3. The subject has any physical or psychiatric condition that, in the Investigator's opinion, would warrant exclusion from the study or prevent the subject from completing the study. 4. The subject's wound shows evidence of infection as determined by the Principal Investigator (which may be indicated by presence of: elevated WBC, pus, moderate or greater discharge, abnormal odor, or acute osteomyelitis). 5. Wound with exposed organs or hardware. 6. Wound with burn etiology.
Number of Sites enrolling participants:	1 (NYU Winthrop Hospital)
ACell Study Products:	
 1. Cytal®™ Wound Matrix 1-Layer 2. MicroMatrix®
Participant & Study Duration:	
80 subjects are expected to complete this trial (maximum of 100 may be enrolled). The duration of participation for each subject will be up to a maximum of 55 weeks (1 week screening/treatment; 12 week follow-up; 26 week confirmation of wound closure/recurrence; 52 week final study visit). All visits have protocol stipulated windows.
 
Recruitment and enrollment efforts are expected to last for approximately 12 months, starting in June 2018. The study will end in approximately May 2019, with Last Subject Last Visit expected in May 2020.
 
The actual overall study duration or subject recruitment period may vary.

Statistical Methodology:	The objective of this study is to define the trajectory of healing using either 1 or 2 test products; the intra-patient change will be the focus

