	
of the analyses, not the comparison of response between 1 vs. 2 product application.
 
All statistical tests to examine the change from baseline (study pre-treatment) will be conducted using a type 1 error rate of 5%. Simultaneous testing for the 2 primary endpoints will be conducted based on individual a priori thresholds. The analyses of the secondary endpoints will be conducted without adjustment for multiple testing.
 
The analysis of the primary endpoints will be based on a generalized linear model specifying the distribution as binomial. If a patient withdraws prior to completing the study, however the last recorded observation revealed the wound had closed, the patient will be counted in the primary analysis as having achieved complete wound epithelization. If a patient withdraws prior to the 12-week wound evaluation visit and the last recorded observation revealed the wound had not closed, the patient will be counted in the primary analysis as not having achieved complete wound epithelization. This procedure will be also be followed for the examination at the patients by the various percent reduction thresholds. The analyses of all non-primary endpoints will be based on the distribution of data. For continuous variables, descriptive statistics will be used and the change from baseline will be tested against a difference of zero. For binomial and multinomial variables, results will be presented using counts, percentages, and shift tables. The analysis of the time of the initial observation of complete wound epithelization will be reported using Kaplan-Meier estimates.

--	--

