4. STUDY DESIGN AND ENDPOINTS

4.1 DESCRIPTION OF THE STUDY DESIGN

This study is a single-site, prospective, observational study of Cytal® Wound Matrix alone or in combination with MicroMatrix® for management of wounds. Cytal® and MicroMatrix® both consist of decellularized porcine urinary bladder matrix (UBM). The processed UBM retains native extracellular matrix structure with intact epithelial basement membrane and numerous collagens that may promote improved wound healing. Cytal® consists of single- or multilayer sheets of UBM, while MicroMatrix® is a micronized powder form of UBM. Both products are FDA 510k cleared (K152721 and K060888) for use in the management of wounds.

In this study, Cytal® Wound Matrix 1-Layer will be applied to study wounds, with MicroMatrix® applied topically to fill the base of deep wounds (exceeding 3mm in depth) according to product use instructions. Patients with diverse wound types will be observed in the study, including but not limited to patients with venous ulcers, diabetic foot ulcers, pressure ulcers, trauma wounds, external surgical wounds, and wound dehiscence/surgical site infection.

Patients may undergo weekly treatment for their wounds and can be treated with up to 10 applications of Cytal® (with MicroMatrix® when wound depth exceeds 3mm) within the first 12 weeks. If the Subject has multiple wounds, the most-appropriate wound that meets inclusion criteria and has at least two cm of healthy tissue between itself and other wounds (as determined by the investigator) will be selected as the Study Wound. A protocolized standard of care will be followed for Study Wounds in addition to the application of Cytal® and MicroMatrix® (i.e. surgical debridement, offloading etc. as appropriate for the particular wound type and severity).

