4.1.1 PRIMARY ENDPOINT

1. Effect of Cytal® with or without MicroMatrix® on primary measures of wound healing efficacy will be assessed by determining:

- a. Number and percentage of wounds with area reduced by greater than or equal to 40% by week 4, 60% by week 8, and 80% by week 12 as determined by wound image planimetry for each wound type.
- b. Number and percentage of completely healed wounds (100% epithelialization) by 12 weeks for each wound type. This will be verified by investigators and through a blinded review of wound photos by independent wound physicians.

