5.3 STRATEGIES FOR RECRUITMENT AND RETENTION

80 subjects (maximum of 100 enrolled) are expected to complete the trial after an approximate 20% dropout/withdrawal rate. The enrollment process will take place over a 12 month period

between June 2018 and May 2019, with all subjects expected to have completed the study by May 2020. All eligible patients will be selected for participation from within NYU Winthrop Hospital, including the outpatient Wound Healing Center clinic.

Patients will be compensated for participation in the trial. Patients will receive one \$25 gift card for each study visit (1 – 12), as well as a \$50 gift card for both the Long-Term Follow-Up visit at Week 26 and the Final Study visit at Week 52.

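### The precision figure that supports N does not match its own table, and the closing power statement covers a two-arm comparison that no specified analysis makes

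*Combined protocol and SAP*

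**What the plan says.** **Basis of N.** Section 10.1 says the sample size was derived from precision, so that the effect of the products, alone or in combination, can be estimated reliably. It puts the distance from a proportion to its two-sided 95% limit, with 80 patients, at 9% to 10%, and refers to a five-row table of exact limits.

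**Closing summary.** The same section ends by describing N as "sufficient to detect a 34% difference in the proportion of responders between the 2 treatments". Power is 81.9% for 30% vs 64% and 81.1% for 15% vs 46%, each with 40 per arm. A third case begins "If there is an imbalance between the 2 treatment arms (30 patients and 50 patients, respectively" and gives 80.3% for 15% vs 47%.

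**Design.** The synopsis and section 4.1 describe a single-site observational study. Every study wound is to receive Cytal, "with MicroMatrix® applied to fill the base of deep wounds (exceeding 3mm in depth". Section 4.1 repeats the depth rule: patients "can be treated with up to 10 applications of Cytal® (with MicroMatrix® when wound depth exceeds 3mm) within the first 12 weeks".

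**Analysis focus.** The synopsis, under Statistical Methodology, says "the intra-patient change will be the focus" of the analyses, "not the comparison of response between 1 vs. 2 product application".

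**Denominator.** Section 5.3 says "80 subjects (maximum of 100 enrolled) are expected to complete the trial after an approximate 20% dropout/withdrawal rate". Section 10.2 estimates 80 treated, with a maximum of 100.

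**Reporting level.** Section 4.1.1 reports both primary endpoints by wound type, for example "Number and percentage of completely healed wounds (100% epithelialization) by 12 weeks for each wound type".

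**The concern.** The two halves of the justification have different faults.

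The precision sentence is the stated reason for choosing 80, and the table beside it contradicts it. One row also appears to use a different number of patients from the others.

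The power paragraph is introduced as the summary of the justification, yet it concerns a contrast between two treatment arms. The study has no arms, and the analysis section describes no test that the power would belong to. A reader could cite the study as having about 80% power to compare Cytal alone with Cytal plus MicroMatrix, which is not what the design or the synopsis sets out to do.

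**Working it through.** **1. Table rows against exact limits.** Inputs are the five printed rows in section 10.1. The exact (Clopper-Pearson) limits for x responders out of n are: lower = the 2.5% quantile of Beta(x, n−x+1); upper = the 97.5% quantile of Beta(x+1, n−x).

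| Scenario | Printed limits | Count that reproduces them | Distance below | Distance above |
|---|---|---|---|---|
| 1 (25%) | 15.99–35.94 | 20/80 | 9.01 | 10.94 |
| 2 (37.5%) | 26.92–49.04 | 30/80 | 10.58 | 11.54 |
| 3 (40%) | 30.33–50.28 | 40/100 | 9.67 | 10.28 |
| 4 (62.5%) | 50.96–73.08 | 50/80 | 11.54 | 10.58 |
| 5 (75%) | 64.06–84.01 | 60/80 | 10.94 | 9.01 |

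- Scenarios 1, 2, 4 and 5 reproduce to two decimals at n=80. Their distances run from 9.01 to 11.54, and 6 of the 8 exceed 10.
- Scenario 3 at n=80 would be 32/80, which gives 29.20–51.56 (distances 10.80 and 11.56). The printed row reproduces at n=100.
- Over every possible count, the largest distance is 11.57 at n=80 and 10.29 at n=100. The stated upper figure of 10 is therefore exceeded at either denominator.
- A symmetric normal half-width does not rescue the sentence. At n=80, 1.96 × √(p(1−p)/80) is 9.5 points at 25% and 10.7 at 40%.

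The companion statement for means is correct. With SD 10 and n=80 the standard error is 10/√80 = 1.118, and a distance of 2 units gives 92.6% confidence (92.3% with the t distribution), which is above 90% as stated.

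**2. The power figures.** Inputs are the three scenarios in section 10.1, with alpha 5%. Sidedness is not stated, so two-sided is assumed. The formula is the normal approximation with pooled null variance and continuity correction:

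power = Φ[(d − c − 1.96·s0)/s1], where d is the difference, c = (1/n1 + 1/n2)/2, s0 = √(p̄(1−p̄)(1/n1 + 1/n2)) and s1 = √(p1(1−p1)/n1 + p2(1−p2)/n2).

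- 30% vs 64%, 40/40: d = 0.34, c = 0.025, s0 = 0.1116, s1 = 0.1049. Power is 82.1% (stated 81.9%).
- 15% vs 46%, 40/40: d = 0.31, c = 0.025, s0 = 0.1030, s1 = 0.0969. Power is 80.5% (stated 81.1%).
- 15% vs 47%, 30/50: d = 0.32, c = 0.0267, s0 = 0.1102, s1 = 0.0961. Power is 79.0%, or 81.2% if the two group sizes are exchanged (stated 80.3%).

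Fisher's exact test gives 83.6%, 81.8% and 84.1%. No single method matches all three, but the stated figures are reasonable two-group powers.

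**3. Is there an analysis they belong to?** Section 10.1 gives a binomial generalized linear model for the primary endpoints without listing its terms, tests of change from baseline against zero, descriptive tables, and Kaplan-Meier estimates. None is described as a comparison between product groups.

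The split is also left to wound depth. For 30% vs 64%, the same formula gives 82.1% at 40/40, 67.8% at 20/60 and 39.4% at 10/70. The last two splits are assumed for illustration; the documents give no expected share of deep wounds.

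**The case against.** **A product comparison is not ruled out.** The synopsis says only that it is not the focus, and the model for the primary endpoints lists no terms, so a product term is unspecified rather than excluded. This stands. A reader might infer that the plan forbids or rejects such a comparison. The text supports only that no between-product test is specified.

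**Estimates by product use are part of the stated purpose.** Section 10.1 wants to estimate effects of the products alone or in combination. This also stands: the remedy should not downgrade those estimates, only remove the implication of a powered test.

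**The precision error is small and visible.** The excess is at most about 1.6 points (11.6 against 10), the reader is sent to the table, and the statement for means is right. That limits the importance of the error but does not make the sentence correct.

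**The denominator is partly settled.** Section 10.1 counts patients who withdraw unhealed as not healed, and section 5.4.2 keeps withdrawn patients' data, which points to all treated subjects. The tension is with section 5.3, which expects 80 completers out of at most 100. The correction to Scenario 3 therefore depends on which denominator is meant.

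**The stated powers are not miscalculated.** A reader might take the 79.0% recomputed for the third scenario as an error. It is not: that result depends on the method and on which group is the larger. The summary also allows for an uneven split through its 30/50 case, though the design does not fix that split either.

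**Conclusion.** The justification is wrong as written in two places.

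- **Precision.** At n=80 the distance to the exact limit is about 9 to 11.6 points over the tabulated proportions, not 9 to 10, and one of the five rows uses 100 patients. This follows from the printed table and needs no outside assumption.
- **Power.** The 80–82% power corresponds to no specified analysis and assumes group sizes that the design does not control. The fault is relevance, not arithmetic. The recomputation assumes a two-sided 5% test.

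A reader might go further and infer that 80 patients are too few. The documents do not support that. They set no precision target that 11.6 points would miss, and the statement for means holds. Precision within each wound type will be lower than the pooled figure, but the documents give no sizes by wound type, so the loss cannot be quantified.

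**What to change.** 1. **Section 10.1, precision sentence.** Replace the 9–10% range with: about 9 to 11.6 percentage points over the tabulated proportions at n=80 (at most 10.3 at n=100), for the cohort pooled over wound types.
2. **Section 10.1, table.** State the denominator and use it in every row. With the stated 80 patients, change Scenario 3 to 29.20–51.56. If 100 is meant, keep Scenario 3 and recompute the other four rows: 25% becomes 16.88–34.66 and 75% becomes 65.34–83.12. The 37.5% and 62.5% rows need new proportions, because neither gives a whole number of patients out of 100.
3. **Section 10.1, closing summary.** Delete the three power figures or label them illustrative. Add that the study is not designed or powered for a formal comparison of Cytal alone with Cytal plus MicroMatrix, and that estimates by product use may still be reported with their confidence intervals.
4. **Optional.** Note, without assumed numbers, that precision within each wound type will be lower than the pooled figure.

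The cost is a slightly less favourable precision figure and the loss of a power claim with no matching analysis. N, endpoints, specified tests and procedures do not change.
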